Title: Self-Affirmation in the Context of Stigma-Induced Identity Threat Among Smokers

NCT03863795

Document Creation Date: February 2, 2019

Approved by Office of Human Subjects Research Protections (OHSRP) NIH: February 4, 2019

Title: Self-affirmation in the context of stigma-induced identity threat among smokers

Description: The purpose of this study is to examine if self-affirmation attenuates the effects of cigarette smoking stigmatization on smoking risk perceptions, pro-smoking beliefs, and intentions to change smoking behavior. The study, including recruitment, pre-screening, the survey, and remuneration, will be conducted on-line. Amazon Mechanical Turk (MTurk), an on-line crowdsourcing program, will be responsible for recruitment, pre-screening, and providing participant remuneration using unique alphanumeric codes. Amazon MTurk will recruit 1,100 US adult smokers. Although the study will be deployed through Amazon MTurk, the survey will be hosted on SurveyGizmo, an on-line survey software platform. No personal identifiers will be collected and neither Amazon MTurk nor SurveyGizmo will have access to personal identifiers as a part of this process. Individual participants' responses will be accessible to only the National Cancer Institute (NCI) investigators to enable data analysis.

Narrative Template for Educational, Survey or Interview Research

Please answer the questions below and upload this document as a MS Word attachment into the web-based system under 'Project Description'. Be sure to discuss in detail the role of the NIH research team and every other entity who will assist or collaborate in the research, including companies with whom you are subcontracting. Collaborators or subcontractors, who are not NIH employees and who are conducting the research off-site, will commonly need IRB approval or an exemption from their own IRB of record.

Remember to also upload a copy of any recruitment scripts, screening questions, survey, interview, or focus group questions or scripts as well as the consent language that will be used for your project into the system. Note that the functionality in the system only allows one document per upload. If you have more than three documents to upload into one section, you may combine them into a single PDF and upload that instead.

1. What is the research question or purpose of this research activity?

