identity threat occurs when people worry that they will be ostracized, repudiated, or stereotyped due to the devalued status of their social identity. Applied to smoking, the model posits that stigma-relevant situational cues (self-threats related to smoking), personal characteristics (individual attributes that relate to situation appraisal; e.g., smoking self-concept), and collective representations (shared meanings related to deprecated statuses in society; e.g., culture, socioeconomic status) converge to predict volitional (intentional behaviors; e.g., smoking cessation) and non-volitional responses to stigma (involuntary, visceral reactions; e.g., mean arterial pressure, cognitive depletion).

The model of stigma-induced identity threat has been previously applied to examine differential responses to stigma-relevant cues among Danish and American smokers who possess varying strengths of smoking self-concept (a measure of smoker identity). Results indicated that regardless of culture, stigmatization was associated with emotional, attitudinal, and cognitive reactions that were counterproductive to eventual smoking cessation (Helweg-Larsen, Sorgen, & Pisinger, forthcoming 2019), but revealed somewhat inconsistent response patterns related to interactions between culture, stigma, and smoking self-concept, which may be illuminated by examining other personal characteristics within the context of this model. To date, no research has examined self-affirmation using the model of stigma-induced identity threat, much less among smokers. Research examining how daily cigarette consumption (a question within the Fagerstrom Test for Nicotine Dependence), and smoking self-concept moderate the effects of self-affirmation on responses to cigarette warning labels, found that high daily cigarette consumption and smoking self-concept were associated with defensive responses (Dillard et al., 2005). Smokers who have recently attempted to quit and current smokers (who have not recently attempted to quit) perceive their risk of developing smoking-related diseases as different (McCoy, Gibbons, Reis, Gerrard, Luus, & Sufka, 1992). Furthermore, a growing body of evidence suggests that the presence of spontaneous self-affirmation, individual differences in the tendency to self-affirm, produces similar responses invoked by self-affirmations (Pietersma & Dijkstra, 2011), but more research is needed to understand how spontaneous self-affirmation may differ from self-affirmations.

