The current project seeks to apply the model of stigma-induced identity threat to explicate how self-affirmation and stigma may interact to shape smokers' perceived risk of developing smoking-related diseases, pro-smoking beliefs, and intentions to change smoking behavior in an empirical paradigm, while controlling for nicotine dependence, daily cigarette consumption, quit attempts, spontaneous self-affirmation, and smoking self-concept.

The purpose of this study is to examine if self-affirmation attenuates the effects of cigarette smoking stigmatization on smoking risk perceptions, pro-smoking beliefs, and intentions to change smoking behavior. Our hypotheses are as follows:

Hypothesis 1: Self-affirmation and smoking stigma will interact, such that among participants in the stigmatizing condition, those who self-affirm will rate their perceived risk of developing smoking-related diseases as higher.

Hypothesis 2: Self-affirmation and smoking stigma will interact, such that among participants in the stigmatizing condition, those who self-affirm will endorse fewer pro-smoking beliefs.

Hypothesis 3: Self-affirmation and smoking stigma will interact, such that among participants in the stigmatizing condition, those who self-affirm will report greater intentions to change smoking behavior.

2. Describe the target population, including the number of planned participants. Subject selection must be equitable or otherwise justified here. (See *NIH HRPP SOP 6, 6.12*.)

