We propose collecting data from 1,100 US current smokers over the age of 18. This estimate was calculated using G*Power (version 3.1.9.2), an open-source statistical power analysis program, in which we set the effect size at $f^2 = .10$ (between small and medium, according to Cohen, 1988), power to .80, alpha to .05, and found that we needed 1,100 participants total. The recruitment platform, Amazon Mechanical Turk (MTurk) is a participant pool comprised of individuals over the age of 18. Due to privacy concerns, Amazon MTurk is not able to disclose the number of participants within their pool who fulfill our study criteria. However, we expect that collecting data from the target population will be feasible given that Amazon MTurk has a predefined cohort of smokers, laboratories sample 7,300 Workers on average (Stewart et al. 2015), and researchers estimate that there are 250,000 US Workers (Bauhoff, Montero, & Scharf, 2017). No other inclusion criteria will be imposed. Amazon MTurk charges an overall fee of 40.0% and a \$0.30 fee per assignment to pre-screen for smoker status. We would like to pay Workers \$6.50 an hour and estimate it will take them 20 min to complete the survey, which equates to \$2.17 per assignment, for a total of \$3,803.10 for 1,100 participants.

3. Which entity(ies) will conduct recruitment? How will it be conducted (telephone, email, regular mail, on-line, in person or some combination of these)? If one entity will simply send out a link through a mass mailing, state that. Will that entity receive and/or maintain any personal identifiers as part of this process? If so, what type of identifiers? (See the list of possible identifiers is included in *NIH HRPP SOP 5, Appendix 2*.)

Participants will be recruited on-line using Amazon MTurk, an on-line crowdsourcing platform. Amazon MTurk assigns Worker IDs, which are unique 14-character alphanumeric codes unrelated to the participants' identities, to the participants within their pool. Amazon MTurk has access to personal identifiers (e.g., name, physical address) but these will not be accessible to the NCI researchers.

4. If the project involves any pre-screening for eligibility, which entity(ies) will conduct pre-screening? How will it be conducted specifically (telephone, email, regular mail, on-line, in person or some combination of these)? Will that entity receive and/or maintain any personal identifiers as part of this process? If so, what type of identifiers?

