Amazon MTurk will conduct pre-screening on-line. Amazon MTurk allows service requesters to select from a list of “Premium Qualifications,” which are predefined cohorts of participants based on certain criteria, including smoker status. We have indicated that eligible participants are adults who consider themselves cigarette smokers and will limit the study pool to those who have US IP addresses.

5. What type of research procedures will be used? For example, will this project involve surveys, interviews, focus groups, educational tests, etc.? How will data collection be conducted (telephone, email, regular mail, on-line, in person or some combination of these)? If not through a website, which entity(ies) will be conducting the various activities? *If different entities will conduct different parts of the data collection, be clear about which entity will conduct what part.* Will that entity receive and/or maintain any personal identifiers as part of this process?

Westat, a social science research firm, has set up and funded an MTurk account for NCI researchers’ use. NCI researchers will post an external Human Intelligence Task (HIT) on Amazon MTurk, described as a survey on smoking attitudes and behaviors, which will redirect eligible participants to study task on SurveyGizmo, an on-line survey software platform. This project will involve survey procedures and data that will be collected on-line via SurveyGizmo. SurveyGizmo will not collect or maintain personal identifiers as a part of the process. At the end of the survey, respondents will be instructed to enter their Worker ID, and after doing so, they will be provided with a 10-digit confirmation code (YQP0ZTC87C), which they will enter into Amazon MTurk. We will approve submitted work if the respondent’s Worker ID matches and they provided the correct 10-digit confirmation code. Once approved, Amazon MTurk will automatically transfer \$2.17 to each Worker’s earning balance. The \$2.17 does not include the \$0.30 fee for using the smoker premium qualification or the 40.0% MTurk service fee.

Participants who meet pre-screening criteria and click on the link to the external HIT will be provided with informed consent information in addition to the NCI principal investigator’s contact information in SurveyGizmo. Participants will be asked to indicate (electronic) consent to proceed to the study.

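### Does the undefined word 'current' in the target population call for a smoking-status check beyond platform self-identification?

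*Protocol*

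**What the plan says.** The protocol names its population three times. The Description says that "Amazon MTurk will recruit 1,100 US adult smokers". Section 2 says: "We propose collecting data from 1,100 US current smokers over the age of 18", and adds: "No other inclusion criteria will be imposed". Section 4 applies the criterion through the platform's "predefined cohorts of participants based on certain criteria, including smoker status", states that "eligible participants are adults who consider themselves cigarette smokers", and limits the pool to US IP addresses. No recency window, frequency or lifetime quantity is given.

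Two further places bear on the meaning. The background in section 1 cites a study in which smokers who had recently tried to quit and "current smokers (who have not recently attempted to quit) perceive their risk of developing smoking-related diseases as different". The aim in the same section is to estimate the effects while "controlling for nicotine dependence, daily cigarette consumption, quit attempts, spontaneous self-affirmation, and smoking self-concept".

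Section 5 puts questions on smoking characteristics in the survey given before the activities, but does not describe them as an eligibility check. A submission is approved on a matching Worker ID and the correct confirmation code. The form asks for screening questions and survey items to be uploaded separately, and these are not shown.

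**The concern.** Besides adulthood and US location, smoking status is the only thing that decides who enters, and its key word is left open. The one gloss on it, in the background, separates current smokers from those who recently tried to quit and says the two groups see their disease risk differently. Perceived risk is the outcome of Hypothesis 1, so it would matter if the protocol left unclear which group it wants.

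The check described is also loose. A person may consider themselves a smoker while smoking no cigarettes now. From that person, the example item for Hypothesis 3 on cutting the daily number of cigarettes says little about intention to change. If many such people enrolled, the results would describe a wider group than the label suggests, and the interaction could be diluted.

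**Working it through.** **1. Which population do the texts describe?**

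| Place | What it contributes |
|---|---|
| Description | US adult smokers |
| Section 2 | current smokers over 18, and no further criteria |
| Section 4 | adults who see themselves as cigarette smokers, US IP address |
| Section 1, background | narrower sense of the word, describing a cited study |
| Section 1, aim | quit attempts handled as a covariate |

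The first three rows describe one pool in increasing detail. The narrower sense is never adopted as a criterion. It also fits poorly with adjustment for quit attempts, which presupposes that people with and without recent attempts are enrolled. The broad reading is the one that fits every operative sentence.

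**2. The plan's own sample size.** Inputs from section 2: f² = .10, power .80, alpha .05, N = 1,100. For the noncentral F test with λ = N·f², f² = .10 needs N = 81 for a 1-df interaction and 114 for a 3-df test among four groups, so 1,100 is not reproduced. Reading the input as f = .10 (f² = .01) with 3 df gives 1,095, close to 1,100; with 1 df it gives 787. That discrepancy is a separate matter, so both readings are carried forward.

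**3. Dilution.** Let a share p of participants not smoke at present and show a fraction r of the full effect. Neither p nor r is in the documents, so both are assumptions. If they are kept, the effective effect is f·(1 − p(1 − r)) with N = 1,100. If they are excluded, f is unchanged and N = 1,100·(1 − p). The test is the 1-df interaction, since all three hypotheses are interactions in a 2 × 2 design; denominator df = N − 4.

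With f² = .10 as written, λ = 1,100 × .10 = 110. At p = .20 and r = 0 it is still 110 × .80² = 70.4. Power is 1.00 throughout.

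With f = .10, power is .912 at p = 0, and otherwise:

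| p | Keep, r = .5 | Keep, r = 0 | Exclude (N) |
|---|---|---|---|
| 5% | .898 | .883 | .898 (1,045) |
| 10% | .883 | .847 | .882 (990) |
| 15% | .865 | .804 | .863 (935) |
| 20% | .847 | .755 | .842 (880) |

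Keeping and excluding break even where (1 − p(1 − r))² = 1 − p. At p = .10 the square root of .90 is .9487, so .10·(1 − r) = .0513 and r = .487. Exclusion helps only below about half the full effect.

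**4. Cost of holding 1,100 after exclusion.** The budget is $3,803.10 / 1,100 = $3.457 per participant. At p = .10, 1,100 / .90 rounds up to 1,223 workers: 123 extra, about $425.

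**The case for a change.** The strongest contrary case is that eligibility belongs in the protocol, that a definition chosen after the data are in is an avoidable analyst choice, and that one item asked before the activities would settle it at little cost. The 3-df test that seems to have produced 1,100 also has less to spare: with f = .10, its power falls from .802 to .705 if 10% of participants show no effect.

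Part of this stands. The word is undefined, and the narrative gives the smoking items no role in confirming eligibility. The rest does not lead to a change:

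- The 3-df figure is for a test that none of the hypotheses uses, and it assumes both a share and a zero effect that the documents do not supply.
- A recency rule would not merely implement the stated criterion. It would turn away people who meet section 4 as written, and so would sit awkwardly beside the statement that no other criteria apply.
- Self-identification is a defensible criterion here. The model under test concerns threat to a devalued social identity, and smoking self-concept is among the variables controlled for.
- Daily consumption and nicotine dependence are planned covariates, so the unseen items may already record someone who smokes nothing. Screening before assignment would also disturb payment, because the step that releases the confirmation code comes late: "At the end of the survey, respondents will be instructed to enter their Worker ID".

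**Conclusion.** No change to the plan is needed. Followed as written, the trial gives an unbiased randomised comparison in self-identified adult cigarette smokers in the US, and the documents point to that population despite the undefined word. The amount of dilution cannot be estimated from them. At the stated f² = .10 it does not matter for any share up to 20%. At f = .10, an assumed 10% share costs between .029 (.912 − .883) and .065 (.912 − .847) of power, of which an exclusion rule recovers nothing at half effect and .035 (.882 − .847) at no effect. These figures assume a common residual variance, the 1-df interaction test and the shares shown.

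The gap is one that analysts can fill sensibly: describe the sample as self-identified smokers and, if the items asked before the activities capture it, report the share with zero daily consumption. Using one population description throughout would be tidier, but nothing in the inference depends on it.

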Participants will be instructed to complete the post-activity survey and respond to questions related to their perceived risk of developing smoking-related diseases (e.g., “What is your chance of getting lung cancer in your lifetime?”, “Imagine that you in the future smoke a pack of cigarettes per day. What is then your chance of getting lung cancer in your lifetime?”; *Not at all likely* to *Extremely likely*), pro-smoking beliefs (e.g., “I enjoy smoking too much to give it up,” “You have got to die of something, so why not enjoy yourself and smoke?”; *Strongly disagree* to *Strongly agree*), intentions to change smoking behavior (e.g., “How likely is it that in the next 6 months you will reduce the number of cigarettes you smoke in a day?”, “How likely is it that in the next 6 months you will seek counselling/support to help you quit smoking?”; *Definitely will not* to *Definitely will*), and demographics (e.g., “What sex were you assigned at birth, on your original birth certificate?”; *Male, Female, Intersex, Other*).

NCI researchers will manage the process of data collection and will respond to participant inquiries via an NIH-designated email account as they arise.

Only answer question #6 if contact information for the NIH staff will be provided to subjects in case they have questions about the research OR if NIH staff will be interacting with subjects for this project; for example:

- a. *to conduct screening or consent;*
- b. *to invite them to participate in the research;*
- c. *to email them a web link to access a survey;*
- d. *to mail a paper copy of a survey; or*
- e. *to collect data via interview/focus group, etc.*

When contact information for NIH staff is being provided, or NIH staff are interacting with potential subjects, you must provide information to subjects that includes certain elements of informed consent for research and upload it in the system. (See “Required Elements of Consent Language” below.)

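### Does a lifetime-risk item that leaves future smoking open undermine the single direction predicted in Hypothesis 1?

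*Protocol*

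**What the plan says.** Question 1 of the protocol states three interaction hypotheses. For participants shown the stigmatizing video, Hypothesis 1 says that "those who self-affirm will rate their perceived risk of developing smoking-related diseases as higher", and Hypothesis 3 that "those who self-affirm will report greater intentions to change smoking behavior". Each gives one direction to a whole construct.

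Question 5, in the description of the post-activity survey, illustrates the constructs with sample items, introduced as examples. For perceived risk there are two. One is "What is your chance of getting lung cancer in your lifetime". The other begins "Imagine that you in the future smoke a pack of cigarettes per day" and then asks for the lung cancer chance under that premise. For intentions, one example is "How likely is it that in the next 6 months you will reduce the number of cigarettes you smoke in a day".

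Question 1 also says that the relation is studied "while controlling for nicotine dependence, daily cigarette consumption, quit attempts, spontaneous self-affirmation, and smoking self-concept". The background notes that smokers with and without a recent quit attempt "perceive their risk of developing smoking-related diseases as different", without saying which group rates its risk higher. Question 2 gives the sample size: "alpha to .05, and found that we needed 1,100 participants total".

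The protocol does not say how the risk items are scored or combined. It does not say how a null result on any single item would be read.

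**The concern.** The two risk items ask different things. The pack-a-day item holds future smoking constant, so a higher rating means that the person accepts more of the message. The open item lets respondents fold in their own plans. If affirmation works and Hypothesis 3 is true, affirmed smokers may expect to smoke less and may honestly rate their own lifetime risk no higher than before. Hypotheses 1 and 3 could then pull against each other on that item.

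The planned covariates would not help. They are participant characteristics, and adjusting for them does not remove a change of plans caused by the activity.

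At stake is the reading of a null. It could mean that affirmation failed, or that it succeeded and changed what people expect to do. If the study rested on the open item alone, it could not tell these apart.

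**Working it through.** **What the text commits to.** The concern needs the protocol to test the open item by itself, or to treat a null on it as evidence of defensiveness. Hypothesis 1 is about the construct. Question 5 lists both items as illustrations of that construct. Neither place singles out the open item. The item that would separate the two readings is already in the survey.

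**Whether the offset is established.** The intention examples concern the next 6 months; the risk item concerns a lifetime. Nothing in the protocol says that the first lowers the second. The remark on quit attempts has no direction. Higher perceived risk may itself raise intentions, in which case there is no attenuation.

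**The plan's own figure.** With the noncentral F, noncentrality λ = N·f² and alpha .05, f = .10 with 3 numerator df reaches power .80 at N = 1,095, close to the stated 1,100. The protocol prints f² = .10, which would need only 81 (1 df) or 114 (3 df). That mismatch is a separate matter. For the 1-df interaction, f = .10 at N = 1,100 gives power .912.

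**How much the offset could cost.** The protocol gives no item-level effects, so these inputs are assumptions:

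- N = 1,100, equal cells, two-sided alpha .05, df 1 and 1,096.
- Direct affirmation-by-stigma contrast of 0.4 SD on each risk item. For a 2×2 interaction f = contrast/4, so this is f = .10.
- Contrast on intention c = 0.4 SD.
- Path b: SD of open-item risk per SD of intention, sign unknown.
- The pack-a-day premise blocks the path.
- Inter-item correlation ρ = .6.

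Open item: u = 0.4 + c·b. Two-item average, in its own SD units: a = [(0.4 + u)/2] / √((1 + ρ)/2).

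Worked case, b = −0.3:

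- Open item: u = 0.4 − 0.12 = 0.28; f = .07; λ = 1,100 × .0049 = 5.39; power .640; null chance .36.
- Average: a = 0.34/√0.8 = 0.380; f = .095; λ = 9.93; null chance .12.

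| b | Null, open item | Null, pack-a-day item | Null, two-item average |
|---|---|---|---|
| +0.3 | .01 | .09 | .01 |
| 0 | .09 | .09 | .04 |
| −0.1 | .15 | .09 | .06 |
| −0.3 | .36 | .09 | .12 |
| −0.5 | .62 | .09 | .21 |

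The protocol's planned type II error is 1 − .80 = .20.

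**Sensitivity of the average.**

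- c = 0.2: .07 at b = −0.3 and .10 at b = −0.5.
- c = 0.6: .18 and .36.
- c = 0.4 and b = −0.5: .16 at ρ = .4, about .26 at ρ = .8.

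**Average against the pack-a-day item alone.** With c = 0.4, setting a = 0.4 gives b = 2(√((1 + ρ)/2) − 1), which is −0.33, −0.21 and −0.10 at ρ = .4, .6 and .8. For any b above (less negative than) these values, the average is the more powerful of the two.

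**The case for a change.** The strongest reply is that the ambiguity on the open item is real and cheap to guard against. Suppose affirmation does not reduce defensiveness but Hypothesis 3 still holds. The open item then carries a contrast of c·b only. With c = 0.4 it is null with chance .83 at b = −0.3 and .62 at b = −0.5. The corresponding chances when Hypothesis 1's direct effect is real are .36 and .62. A null on the open item therefore favours failed affirmation by only .83/.36 = 2.3 to 1 in the first case and .62/.62 = 1.0 to 1 in the second. Taken alone, the item can become uninformative. Splitting the items only after a null would also look post hoc.

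That stands as a remark about one item under a strongly negative path. It does not show an error here. The path has no support in the document, and nobody proposes to use the item alone. Item-level reporting and rules for reading results are commonly left to the statistical analysis plan, which is not at hand.

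A caution written only for nulls would also be one-sided, since it makes Hypothesis 1 harder to refute. And the pack-a-day item is not necessarily clean. For a light smoker it is hypothetical, and answers could pile up at the top of the scale, so a null there could be ambiguous too.

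**Conclusion.** The concern does not hold. The protocol gives one direction to a construct, illustrates that construct with two complementary items, and draws no conclusion from either item by itself. Nothing is stated wrongly or contradicted.

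Under the illustrative assumptions (0.4 SD contrasts, ρ = .6, N = 1,100), a combined score has a null chance of .04 to .21 for b from 0 to −0.5, at or below about the .20 the protocol accepts. It exceeds .20 clearly only where a strong negative path meets a large intention effect (.36) or a high inter-item correlation (about .26). These figures rest on assumed effects and on an equal-weight average, which the protocol does not specify. The conclusion does not depend on them: the reading under attack is not in the document, and the direction of the supposed offset cannot be determined from it. Reporting the two items separately would be a reasonable preference, but it would leave Hypothesis 1, its direction, its outcome and both items as they are.
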